6.3.2 Definitions of serious adverse event

A serious adverse event is an AE occurring during any study phase (i.e., run-in, treatment, washout and follow-up), that fulfils one or more of the following criteria:

- Results in death
- Is immediately life-threatening
- Requires in-patient hospitalisation or prolongation of existing hospitalisation
- Results in persistent or significant disability or incapacity
- Is a congenital abnormality or birth defect
- Is an important medical event that may jeopardise the subject or may require medical intervention to prevent one of the outcomes listed above.

For further guidance on the definition of a SAE, see [Appendix B](#) to the Clinical Study Protocol.

6.3.3 Recording of adverse events

Time period for collection of adverse events

Adverse Events will be collected from the time study drug is first administered throughout the treatment period and including completion of scheduled study procedures.

SAEs will be recorded from the time of informed consent.

Follow-up of unresolved adverse events

Any AEs that are unresolved at time of the final scheduled study assessment are to be followed up by the investigator for as long as medically indicated, but without further recording in the eCRF. AstraZeneca retains the right to request additional information for any subject with ongoing AE(s)/SAE(s) at the end of the study, if judged necessary.

Variables

The following variables will be collect for each AE:

- AE (verbatim)
- The date and time when the AE started and stopped
- Intensity
- Whether the AE is serious or not
- Investigator causality rating against the Investigational Product (yes or no)
- Action taken with regard to investigational product
- AE caused subject's withdrawal from study (yes or no)
- Outcome

In addition, the following variables will be collected for SAEs:

- Date AE met criteria for serious AE
- Date Investigator became aware of serious AE
- AE is serious due to
- Date of hospitalisation
- Date of discharge
- Probable cause of death
- Date of death

- Autopsy performed
- Causality assessment in relation to Study procedure(s)
- Causality assessment in relation to Other medication
- Description of AE

It is important to distinguish between serious and severe AEs. Severity is a measure of intensity whereas seriousness is defined by the criteria in Section 6.3.2. An AE of severe intensity need not necessarily be considered serious. For example, nausea that persists for several hours may be considered severe nausea, but not a SAE. On the other hand, a stroke that results in only a limited degree of disability may be considered a mild stroke but would be a SAE.

In case seizures, haemolytic anaemia, renal failure and DILI (drug-induced liver injury) occur during the study, irrespective of their seriousness, additional information will be requested and collected by way of targeted follow-up questionnaires in the WBDC (Web Based Data Capture) system or by manual intake forms. Details regarding these questionnaires may be found in [Appendix B](#).

Causality collection

The Investigator will assess causal relationship between Investigational Product and each Adverse Event, and answer 'yes' or 'no' to the question 'Do you consider that there is a reasonable possibility that the event may have been caused by the investigational product?'

For SAEs causal relationship will also be assessed for other medication and study procedures. Note that for SAEs that could be associated with any study procedure the causal relationship is implied as 'yes'.

A guide to the interpretation of the causality question is found in [Appendix B](#) to the Clinical Study Protocol.

Adverse Events based on signs and symptoms

All AEs spontaneously reported by the patient or reported in response to the open question from the study personnel: 'Have you had any health problems since the previous visit/you were last asked?' or revealed by observation will be collected and recorded in the eCRF. When collecting AEs, the recording of diagnoses is preferred (when possible) to recording a list of signs and symptoms. However, if a diagnosis is known and there are other signs or

symptoms that are not generally part of the diagnosis, the diagnosis and each sign or symptom will be recorded separately.

Adverse Events based on examinations and tests

The results from protocol mandated laboratory tests and vital signs will be summarised in the clinical study report. Deterioration as compared to baseline in protocol-mandated laboratory values, vital signs and 12-lead ECGs findings should therefore only be reported as AEs if they fulfil any of the SAE criteria or are the reason for discontinuation of treatment with the investigational product.

If deterioration in a laboratory value/vital sign is associated with clinical signs and symptoms, the sign or symptom will be reported as an AE and the associated laboratory result/vital sign will be considered as additional information.

Wherever possible the reporting investigator uses the clinical, rather than the laboratory term (e.g., anaemia versus low haemoglobin value). In the absence of clinical signs or symptoms, clinically relevant deteriorations in non-mandated parameters should be reported as AE(s).

Any new or aggravated clinically relevant abnormal medical finding at a physical examination as compared with the baseline assessment will be reported as an AE.

NB. Cases where a subject shows an AST or ALT $\geq 3xULN$ or total bilirubin $\geq 2xULN$ may need to be reported as SAEs, please refer to [Appendix E](#) ‘Actions required in cases of combined increase of Aminotransferase and Total Bilirubin – Hy’ s Law’, for further instructions.

6.3.4 Reporting of serious adverse events

All SAEs have to be reported, whether or not considered causally related to the investigational product, or to the study procedure(s). All SAEs will be recorded in the eCRF.

If any SAE occurs in the course of the study, then investigators or other site personnel must inform appropriate AstraZeneca representatives within one day i.e., immediately **but no later than the end of the next business day** of when he or she becomes aware of it, **and report to the Ethics Committee and Regulatory authority based on local drug administration laws and regulations.**

The designated AstraZeneca representative works with the investigator to ensure that all the necessary information is provided to the AstraZeneca Patient Safety data entry site **within one calendar day** of initial receipt for fatal and life threatening events **and within five calendar days** of initial receipt for all other SAEs.

For fatal or life-threatening adverse events where important or relevant information is missing, active follow-up is undertaken immediately. Investigators or other site personnel inform AstraZeneca representatives of any follow-up information on a previously reported SAE within one calendar day i.e., immediately but **no later than the end of the next business day** of when he or she becomes aware of it.

Once the Investigators or other site personnel indicate an AE is serious in the WBDC system, an automated email alert is sent to the designated AstraZeneca representative.

If the WBDC system is not available, then the Investigator or other study site personnel reports a SAE to the appropriate AstraZeneca representative by telephone.

The AstraZeneca representative will advise the Investigator/study site personnel how to proceed.

6.3.5 Laboratory safety assessment

Blood and urine samples for determination of clinical chemistry, haematology and urinalysis parameters will be taken at the times given in the Study Plan (Table 1). The date of collection will be recorded in the appropriate eCRF.

If any of the tests performed on the samples taken after investigational product administration show clinically significantly abnormal results as judged by the investigator, new blood samples will be obtained and tests repeated until the results return to baseline or the cause is assessed. The investigator will provide an evaluation of the clinical importance of the deviation. The development of any clinically relevant deterioration in any laboratory parameter may constitute an AE if it leads to discontinuation of the study drug or if it fulfils the criteria of seriousness. The investigator will record on the laboratory report whether the abnormality is Clinically Significant (CS) or Not Clinically Significant (NCS).

NB. In case a subject shows an AST **or** ALT $\geq 3 \times \text{ULN}$ **or** total bilirubin $\geq 2 \times \text{ULN}$ please refer to [Appendix E](#) ‘Actions required in cases of combined increase of Aminotransferase and Total Bilirubin – Hy’s Law’, for further instructions.

Table 4 Clinical laboratory tests

Haematology	Clinical Chemistry	Urinalysis	Virology (screening only)	Other¹
Haemoglobin	Magnesium	pH	HBV (HBeAg, HBsAg)	Urine pregnancy test for women of child bearing potential
Hematocrit	Bicarbonate	Specific gravity	HCV	
Red blood cell count (RBC)	Sodium	Glucose	HIV	
WBC	Potassium	Ketone		
WBC differential (percentages and absolutes)	Phosphorus	Protein		
Mean corpuscular volume	Chloride	Bilirubin		
Mean corpuscular haemoglobin	Calcium	RBC		
Mean corpuscular haemoglobin concentration	Alkaline phosphates	WBC		
Platelet count	Gamma-glutamyl transferase	Crystals		
Prothrombin time (PT)	ALT	Casts		
PT/international normalized ratio (INR)	AST	Microscopic examination of the sediment if positive for blood or protein.		
Partial thromboplastin time	Lactic dehydrogenase			
Direct Coombs' test	Total bilirubin			
	Total cholesterol			
	Triglycerides			
	Glucose			
	Total protein			
	Albumin			
	Creatine kinase			
	Serum creatinine			
	Urea nitrogen			
	Uric Acid			

¹ If the subject had rash, additional test may be required to understand the immunological disposition of subjects such as HLA typing etc.

For blood volume see Section 7.1

6.3.6 Physical examination

Physical examinations will be conducted according to the schedule outlined in the Study Plan (Table 1).

6.3.6.1 Complete physical examination

The complete physical examination will include an assessment of the following: general appearance, skin, head and neck (including eyes, ears and throat), lymph nodes, thyroid, musculoskeletal/extremities (including spine), cardiovascular, lungs, abdomen, and neurological systems.

Complete physical examination data to be recorded in the eCRF will include:

- Normal
- Abnormal with a description of any abnormalities
- Same as previous

6.3.6.2 Brief physical examination

The brief physical examination will include an assessment of the following items: general appearance, abdomen, lungs, and the cardiovascular system.

Brief physical examination data to be recorded in the eCRF will include:

- Normal
- Abnormal with a description of any abnormalities
- Same as previous

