The safety data reveal that potential adverse cardiac, renal, or hepatic effects with the administration of ceftaroline fosamil were similar to those observed for other cephalosporins. The risk of allergic reactions to ceftaroline appears to be similar to that of the comparators studied. Two seizures were observed in subjects who received ceftaroline fosamil, both occurred more than two days after completion of ceftaroline fosamil therapy. Cephalosporins are known to be associated with positive direct Coombs' test results. The rates of seroconversion from a negative to a positive direct Coombs' test were higher in the ceftaroline group compared with the comparator groups; however no subject was identified with clinical findings or laboratory results that were consistent with haemolytic anaemia. The incidence of potential antibiotic-associated diarrhoea (which can occur with most antibiotics) was low and similar in subjects who received ceftaroline fosamil compared with comparator therapies and resulted in similar numbers of subjects prematurely discontinued from study drug or from the study due to TEAEs of diarrhoea in both treatment groups. Confirmed cases of *C difficile*-associated diarrhoea were rare in both treatment groups.

At the clinical dosages studied (600 mg or 400 mg administered as a 60-minute IV infusion q12h) ceftaroline demonstrated an acceptable safety profile that was compatible with treatment of cSSSI and CABP. In addition, no safety concerns were identified in the safety review beyond those already known to be cephalosporin class effects.

Doses of ceftaroline fosamil higher than those studied in the Phase 3 program (eg, single doses up to 2000 mg and multiple doses up to 1800 mg/day [either q12h or q8h]) have been studied in a Phase 1 study (P903-20) and in a Phase 1 ceftaroline fosamil/avibactam study (CXL-PK-01). The safety of these higher doses of ceftaroline fosamil was consistent with that observed at the 600 mg q12h dose used in the Phase 2 and Phase 3 cSSSI and CABP studies.

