3.1 Overall study design and flow chart

This is a phase I, single centre and open label study, to assess the PK and safety of ceftaroline following single and multiple administration of 600 mg ceftaroline fosamil as 60-minute IV infusion q12h and as 120-minute intravenous infusion q8h in healthy male and female Chinese volunteers. Approximately 24 healthy volunteers will be entered into two groups to obtain at least 10 evaluable subjects for each group. An evaluable subject is defined as a volunteer completing all study procedures from the screening period to the final blood sampling time point for plasma levels of ceftaroline on Day 10 (Group I) or Day 9 (Group II).

The timing of study assessments is outlined in the Study Plan (Table 1). Subjects will undergo screening assessments during the 21-day period preceding administration of the first

dose of study drug on Day 1. Subjects will report to the study unit the day before administration of the first dose of study drug (Day -1) and will remain confined there until completion of study procedures on Day 10 (Group I) or Day 9 (Group II). In addition, subjects will return to the CPU for a follow up visit approximately 5-10 days after the discharge from the CPU. Each subject's participation, including the screening period, will take 41 days (Group I) or 40 days (Group II).

This study will be conducted in two groups of healthy volunteers. The groups will be recruited sequentially.

Group I: 12 healthy volunteers will receive a single 600 mg ceftaroline fosamil as 60-minute IV infusion in the morning on Day 1 and 8. On Days 3 -7 volunteers will receive 600 mg ceftaroline fosamil as 60-minute IV infusion q12h. On day 2, the volunteers will not receive drug, but plasma and urine PK sample will be obtained.

Group II: 12 healthy volunteers will receive a single 600mg ceftaroline fosamil as 120-minute IV infusion in the morning on Day 1 and 8. On days 2 -7 volunteers will receive 600mg ceftaroline fosamil as 120-minute IV infusion q8h.

Plasma and urine PK samples will be obtained at the times noted in the PK Plasma and Urine Sampling schedule (Table 2).

Safety assessments including physical examinations, laboratory assessments, 12-lead ECGs, and vital sign measurements will be performed according to the schedule in the Study Plan. If the subject had rash, additional test may be required to understand the immunological disposition of subjects such as HLA typing etc. (Table 1).

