Principal investigator and AstraZeneca appropriate personnel will review the safety data after Group I last subject out, to determine if the next sequential cohort (Group II) may be enrolled as planned. The safety data (including all adverse events and laboratory data collected during the Group I drug administration phase) will be summarized and made available to the ethics committee for endorsement prior to the start of the enrolment of subjects in Group II.

Table 1 Study Plan

Assessment	Visit 1	Visit 2											Visit 3
	Screening Day -21 to -2	Study Day -1	1	2	3	4	5	6	7	8	9	10	Follow up 5-10 days after discharge
Informed consent	X												
Demographics	X												
Inclusion/exclusion criteria	X	X											
Medical/surgical history	X												
Group I													
Complete physical exam	X	X										X	
Brief physical exam			X	X	X	X	X	X	X	X	X		X
12-lead ECG	X	X	X		X		X		X			X	X
Vital signs (BP, pulse, oral temp)	X	X	X	X	X	X	X	X	X	X	X	X	X
Safety labs(Clinical chemistry, Haematology,Urinalysis)	X	X			X				X			X	X
Safety labs(Coagulation)		X										X	X
Safety labs(Coombs)		X										X	X
Pregnancy test	X	X										X	X
Alcohol breath test	X	X											
Drugs abuse screen	X	X											
Virology screen	X												
Ceftaroline fosamil dose ¹			X		X	X	X	X	X	X			

Assessment	Visit 1	Visit 2										Visit 3	
	Screening Day -21 to -2	Study Day -1	1	2	3	4	5	6	7	8	9	10	Follow up 5-10 days after discharge
Ceftaroline fosamil dose ¹		X	X	X	X	X	X	X	X	X			
PK plasma samples ²		X	X	X	X	X	X	X	X	X	X		
PK urine samples ²		X	X							X	X		
Confinement to CPU			←—————→										
AE monitoring			←—————→										
SAE monitoring		←—————→											

¹ The subjects of Group I will receive a single 600 mg dose of ceftaroline fosamil as 60-minute IV infusion in the morning on Day 1 and 8. On Days 3 through 7, subjects will receive 600 mg ceftaroline fosamil q12h. Each IV infusion will be administered as a 60-minute infusion. The subjects of Group II will receive a single 600 mg dose of ceftaroline fosamil as 120-minute IV infusion in the morning on Days 1 and 8. On Days 2 through 7, subjects will receive 600 mg ceftaroline fosamil q8h. Each IV infusion will be administered as a 120-minute infusion

² See [Table 2](#) for PK Plasma and Urine Sampling Schedule.

If the subject had rash, additional test may be required to understand the immunological disposition of subjects such as HLA typing etc.

Table 2 PK Plasma and Urine Sampling Schedule

Sample	Schedule¹

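### The brief physical examination omits skin, so in Group I only 1 of 11 scheduled examinations from Day 1 on lists it, although the protocol plans extra tests for rash

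*Protocol*

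**What the plan says.** Section 6.3.6 hands the timing of examinations to Table 1: "Physical examinations will be conducted according to the schedule outlined in the Study Plan (Table 1"). Two kinds are defined.

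- **Complete** (6.3.6.1): "The complete physical examination will include an assessment of the following: general appearance, skin, head and neck (including eyes, ears and throat"), followed by further body systems.
- **Brief** (6.3.6.2): "The brief physical examination will include an assessment of the following items: general appearance, abdomen, lungs, and the cardiovascular system".

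Three other places bear on skin.

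- Section 3.1, repeated under Table 1 and Table 4: "If the subject had rash, additional test may be required to understand the immunological disposition of subjects such as HLA typing".
- Section 1.1.1, on known safety: "The risk of allergic reactions to ceftaroline appears to be similar to that of the comparators studied". Section 4.2 also excludes volunteers with a history of beta-lactam hypersensitivity.
- Section 6.3.3, on how examination findings become adverse events: "Any new or aggravated clinically relevant abnormal medical finding at a physical examination as compared with the baseline assessment will be reported as an AE".

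The same section 6.3.3 also collects events that volunteers report unprompted, that they give in answer to an open question, or that staff observe.

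**The concern.** Rash is the one clinical sign for which the Study Plan footnotes foresee additional tests. Yet the examination repeated through the dosing period does not list the organ on which rash appears. The rule in 6.3.3 that turns an examination finding into an adverse event works by comparison with baseline. For skin, Group I has baseline examinations but no scheduled comparison until Day 10.

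What is at stake is how completely skin events are recorded and how well their onset is dated. Safety and tolerability is a secondary objective (2.2). The Group I safety data also go into the review, and to the ethics committee, before Group II may be enrolled (6.3.9).

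**Working it through.** No statistical figure in the protocol is involved. The check is a count from Table 1, combined with the two content lists.

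**Inputs**

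- Group I complete examination (Table 1): screening, Day -1, Day 10.
- Group I brief examination (Table 1): Days 1 to 9 and follow-up.
- Group I dosing days (Table 1 and 5.5.2): Days 1, 3, 4, 5, 6, 7 and 8, which is 7 days.
- Skin listed: complete yes (6.3.6.1), brief no (6.3.6.2).

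**Count for Group I from Day 1 on**

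- Brief examinations: 9 (Days 1 to 9) + 1 (follow-up) = 10.
- Complete examinations: 1 (Day 10).
- Total: 10 + 1 = 11.

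| Period | Scheduled examinations | Listing skin |
|---|---|---|
| Baseline (screening, Day -1) | 2 | 2 |
| The 7 dosing days | 7 | 0 |
| Days 2 and 9 (no dose) | 2 | 0 |
| Day 10 | 1 | 1 |
| Follow-up | 1 | 0 |
| **All from Day 1 on** | **11** | **1** |

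**Timing**

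- Group I receives 1 + (5 × 2) + 1 = 12 infusions, the last on the morning of Day 8. The Day 10 examination falls about 10 − 8 = 2 days (48 hours) later.
- Follow-up is 5 to 10 days after discharge on Day 10, so 2 + 5 = 7 to 2 + 10 = 12 days after the last dose. It uses the brief list.

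**Does general appearance already cover skin?** Section 6.3.6.1 puts the two side by side as separate items: "general appearance, skin, head and neck (including eyes, ears and throat"). On the protocol's own usage, the first does not stand in for the second. A site can complete the brief examination as written without a deliberate look at the skin.

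**Scale.** With 12 volunteers in a group, one unrecorded rash changes the observed proportion by 1/12, or about 8 percentage points. This shows how much a single event weighs in a group this small. It is not an estimate of how many would be missed.

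**Group II.** The list in 6.3.6.2 is not specific to a group, so its content applies to both. The Group II examination rows of Table 1 could not be read in the text available, so no count is made.

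**The case against.** The strongest reply is that a brief examination is meant to be shorter than a complete one. Nothing in the protocol promises a daily skin check or makes the rash tests depend on an examination. That stands: this is a weak design choice and not a contradiction.

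The second reply concerns harm. A reader might infer that a rash would come to light only if the volunteer mentioned it, or that nobody looks at the skin while drug is given. The documents do not support either reading:

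- Section 6.3.3 also accepts answers to the open question and events seen by staff.
- Volunteers are confined to the unit until Day 10 (Group I), and dosing is supervised (5.7).
- Group I has 17 plasma sampling times on Day 1 and again on Day 8 (Table 2), taken by venipuncture or in-dwelling catheter (6.5.1.1).
- The brief examination includes general appearance, calls for any abnormality to be described, and covers the abdomen, lungs and heart, so some skin will be seen in passing.

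These points are sound and narrow the gap considerably. They do not close it. The other routes favour what is symptomatic or visible, and a mild rash under clothing may be neither. Once volunteers have left the unit, staff no longer see them day to day, and the follow-up examination does not list skin.

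Third, rash appears in the protocol as a contingency for optional tests and is not among the most common events listed in section 1.3. Infusion-site reaction is not named as a risk. Both remarks are correct, so the case here rests on allergic reaction and the rash provision alone.

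**Conclusion.** The point holds as a minor one. In Group I, skin is listed in 1 of 11 scheduled examinations from Day 1 on, in 0 of 7 on dosing days, and not at follow-up. The count rests on Table 1 as read and on taking skin and general appearance as distinct items, as 6.3.6.1 does.

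The gap is in systematic examination and not in all detection. A mild or covered rash could be missed, or dated later than it began. The protocol gives no basis for saying how often.

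Two further inferences should not be drawn. One is that the extra tests for rash would go undone: they can follow from a rash found by any route, and they are optional. The other is that the same count applies in Group II, which cannot be checked.

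**What to change.** In 6.3.6.2, add skin to the items of the brief examination. Including the infusion site in that item is optional. Leave the Table 1 schedule unchanged.

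The examination is already scheduled, so no visit, sample or procedure is added. The cost is one more item per examination and the matching entry in the eCRF. A few more minor skin findings will probably be recorded as adverse events under 6.3.3, which should be kept in mind when the adverse event tables are read.
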